 **Foundations**

What Works Centre for Children & Families

foundations.org.uk

Pilot RCT of Let's Connect - Fostering Communities

Intervention developer	The Copeland Center and Barnardo's
Delivery organisations	Barnardo's
Evaluator	Coram
Principal Investigator	[name], Head of Impact and Evaluation, Coram
Protocol author(s)	[name], [name], [name], [name], [name], [name] and [name]
Type of trial	Pilot randomised controlled trial (RCT) with 50:50 randomisation at family level to two arms: intervention and control
Age or status of participants	Foster families (foster children, foster carers, and birth children of foster carers), kinship carers, and their birth and kinship children
Number of participating sites	3 local authorities – Hull City Council, North Lincolnshire Council, North East Lincolnshire Council
Number of children and families	Target for randomisation: 178 fostering households with 311 foster carers, 544 foster children, 25 other adults, 59 birth children (plus kinship households, numbers unknown)
Primary outcome	1. Foster/kinship carer wellbeing (Warwick Edinburgh Mental Wellbeing Scale)
Secondary outcome(s)	2. Foster/kinship carer perceived peer support (self-reported number of 'other local foster or kinship carers you could ask for help if you needed' (0+)) 3. Foster child, kinship child and birth child mental health and wellbeing (Brief Assessment Checklists for Children and Adolescents;

	Strengths and Difficulties Questionnaire – available for foster children only 4. Foster/kinship family relationships (SCORE-15) 5. Foster placement stability (number of placement changes)
Exploratory outcome(s)	6. Foster carer turnover 7. Mental health referrals (referral of foster/kinship children to CAMHS)
Contextual factors	Receipt of other mental health and emotional wellbeing support and services Extent of existing community connections and networks among foster and kinship families

Summary

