Families who express an interest in taking part in the WRAP programme and its evaluation will be randomised to either a referral, or usual support for mental health and wellbeing, which includes providing information about existing services (50:50 split).

Randomisation will be at the family level. This means all household members in the intervention group will be referred. Barnardo’s aims to reach as many of the members of each target family as wish to take part. We believe this choice of unit will help address ethical and logistical concerns around randomisation (such as sibling dynamics). Having taken advice on terminology from advisors, we will avoid the use of ‘intervention group’ and ‘control group’ in communications with families.

We have outlined participants’ journey through the trial in the CONSORT diagram in Figure 2. This is based on the sample of participants available across the three local authorities. Foster families are more numerous than kinship families and will be prioritised by Barnardo’s, so our numbers below cover foster families and represent minima. We have included a separate CONSORT diagram with our estimation of kinship households in Annex 1, but do not want to rely on this given the lack of available data on the number of kinship carers. We have built the following assumptions into our estimations:

- 3% of households will be ineligible on the basis that there is at least one child in the household with an urgent or emergency mental health referral. This is an estimation based on the proportion of under-18s with an emergency referral, and an elevated level of mental health need in foster children⁷.

⁵ Rubin, D. M., O’Reilly, A. L. R., Luan, X., and Localio, R. (2007) ‘The Impact of Placement Stability on Behavioral Well-being for Children in Foster Care,’ *Paediatrics*, 119(2): 336-344.

⁶ Adams, E., Hassett, A. R., and Lumsden, V. (2018) ‘What do we know about the impact of stress on foster carers and contributing factors?’ *Adoption & Fostering*, 42(4): 338-353.

[figure not shown]
⁷Looked-after children and young people, NICE guideline (2021): www.nice.org.uk/guidance/ng205/chapter/Context

- 55% of invited households attend info session. This is a conservative estimate based on engagement experience of previous interventions in foster communities, i.e. foster carers being busy, having many commitments etc.

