Total approved fostering households ¹¹	200	105	110	415
Number of foster carers in approved fostering households ⁷	360	175	190	725
Number of looked-after children in foster placements ¹²	661	439	169	1,269

There is no available data on the number of non-foster carer adults or birth children in fostering households. Data leads at the three local authorities informed us that this data is not systematically collected and stored, and is only available through social worker notes. We have assumed one non-foster carer adult per seven fostering households (n=59 other adults), and one birth child per three fostering households (n=138 birth children). The overall pool of fostering households in the three local authorities is therefore 784 adults and 1,407 children.

Following the CONSORT diagram assumptions outlined above, if 95% of all adults and children in intervention trial arm households take part in Level 1 WRAP, this equates to 159 adults and 287 children. As outlined above, kinship carers will be recruited to supplement these numbers and to meet Barnardo's desired delivery of 240 adults and 240 children. We have outlined an approach to mitigate against low uptake rates below.

Inclusion criteria

The trial will include:

- Fostering and kinship households in Hull City Council; North East Lincolnshire Council; and North Lincolnshire Council.
- Fostering and kinship households where at least one adult expresses an interest in taking part in the WRAP programme and its evaluation.
- Fostering households will be prioritised where foster carers are caring for one or more foster children at the time of randomisation.
- Children must be aged nine and over¹³ in order to attend WRAP sessions, but

¹¹ National statistics: Fostering in England 1 April 2021 to 31 March 2022 (2022). Ofsted. www.gov.uk/government/statistics/fostering-in-england-1-april-2021-to-31-march-2022/fostering-in-england-1-april-2021-to-31-march-2022#contacts

¹² National statistics: Children looked after in England including adoptions (2022). Department for Education. <https://explore-education-statistics.service.gov.uk/find-statistics/children-looked-after-in-england-including-adoptions/2022>

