¹³ Barnardo's tell us their experience of delivery of WRAP has largely focused on supporting young people in secondary school, with recent delivery extended to year five and six pupils in Hull. Delivering WRAP to children younger than nine years would require specific permission from the founders and licence holders of WRAP to change aspects of the programme, such as the language used. Barnardo's wants to deliver WRAP to younger children as part of a smaller project before including it in an RCT.

families with younger children can still be randomised (the adult(s) can attend WRAP).

Exclusion criteria

Local authorities will first exclude ineligible families, who:

- Plan to cease fostering in the next year
- Contain at least one child referred for crisis care from CAMHS (urgent or emergency)
- Foster families in crisis and on the verge of placement breakdown

Based on local statistics published by Ofsted we estimate the first criterion would exclude around 25% of families if local authorities had perfect information, but will be approximately replaced by families which start fostering over the same time period. Based on NHS Digital, ONS and DfE data, we assume 19 families will be ineligible due to crisis referrals.¹⁴ Based on March 2021 local Ofsted data, we can expect 1.7 foster carers per foster family and 1.88 foster children per foster family.

Procedures

Local authorities will provide carer contact information to Barnardo's, and Barnardo's will send eligible families an invitation to an information session. Barnardo's will facilitate information sessions, with the aim of giving prospective participants clear information about the programme and evaluation to inform their decision whether to express interest. Delivery of information sessions will be ongoing throughout the programme, and a minimum delivery of two per week is anticipated, with more at certain points e.g. in the start-up period. They will include co-delivery with some fostering and kinship community members after their completion of WRAP Level 1 groups.

After attending an information session, interested participants will complete an Expression of Interest form. Barnardo's will collate these and send the details of these households to Coram for randomisation. We will randomise the stock of families in February 2023, and then on demand as needed for the in-flow of newly eligible families thereafter until early 2024.

Mitigations in case of low uptake

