We will estimate regression models to analyse the two exploratory outcomes. We will use logistic models given the nature of the data; whether or not a foster/kinship child has been referred to CAMHS since randomisation; and whether or not a foster/kinship carer has ceased fostering since randomisation. We will analyse these outcomes according to our pre-specified reason categories but for robustness will also explore the impact on point estimates and effect sizes when alternative categories are used. Relative risk ratios and percentage point changes will be used to express effect sizes.

We expect that some foster children may move, after randomisation, to a household randomised to a different trial arm. We will report on the proportion of children that move between randomised households, in order to estimate the degree of trial arm 'contamination'.

If data allows we will carry out exploratory analysis with sub-groups or include other variables of interest as predictors in regression analyses e.g. whether facilitator was Barnardo's staff member, or trained carer etc. We intend to include whether adults are foster carers, kinship carers, or other adults in the household, and whether children are birth children, kinship children, and foster children. We will also include time from randomisation in months as an interaction with trial arm (included in main regression model as a fixed effect) in order to explore the relationship of time between baseline and endline surveys with outcome differences between intervention and control groups.

In order to understand how well scores on the Strengths and Difficulties Questionnaire recorded by local authorities and scores on the foster-carer reported Brief Assessment Checklist align, we will use a correlation analysis (Spearman's rho and illustrative plots) to explore this.

Compliance

We will explore the influence of trial arm allocation compliance (i.e. whether individuals in the intervention arm receive WRAP, and how many sessions), by including the number of sessions attended in an instrumental variable analysis. Our compliance analysis will look at carer attendance of at least one WRAP session versus non-attendance in terms of change in the primary outcome at individual carer level.

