We will also look at attendance as a proportion of household members (e.g., two out of four household members attending means 0.5 attendance) as an instrumental variable in outcomes, as well as the attendance of children at WRAP sessions in relation to their scores on the SDQ and BAC. We may conduct an exploratory dosage analysis with the number of sessions as the instrumental variable, as opposed to binary non-/attendance.

Analysis of harms

We will analyse the proportion of foster children that demonstrate reliable and clinically significant deterioration between their 'pre' and 'post' SDQ scores. For a clinically significant deterioration we will report the proportion of foster children that move from a pre score of below 17 to above at post-test i.e. the clinical threshold for the SDQ (Goodman, 2001²²; Goodman, Ford, Simmons *et al.*, 2000²³). For reliable deterioration, we will report the proportion of foster children that show an increase in SDQ score from pre to post test that is greater than the reliable change index (Jacobson and Truax, 1991²⁴).

Process evaluation

Evaluation questions

²² Goodman, R. (2001). Psychometric properties of the strengths and difficulties questionnaire. *Journal of the American Academy of Child and Adolescent Psychiatry*, 40(11), pp.1337-1345.

²³ Goodman, R., Ford, T., Simmons, H., Gatward, R., & Meltzer, H. (2000). Using the Strengths and Difficulties Questionnaire (SDQ) to screen for child psychiatric disorders in a community sample. *British Journal of Psychiatry*, 177, pp.534-539.

²⁴ Jacobson, N. S., & Truax, P. (1991). Clinical significance: a statistical approach to defining meaningful change in psychotherapy research. *Journal of Consulting and Clinical Psychology*, 59(1), pp.12-19.

The process evaluation consists of three summative questions under three themes: delivery of the intervention; participant experiences and learning for future delivery:

Delivery of the intervention

- A. To what extent was the intervention implemented as intended compared to the activities detailed in the theory of change and logic model?
- This will consider:
 - What are the core elements of the intervention that was delivered?
 - How does the delivered intervention vary across groups?
 - How is it different to usual support provided to the foster and kinship community?
 - What are the barriers and enablers to successful implementation of WRAP?

Participant experiences

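### The household attendance share counts children under nine, who may not attend WRAP, in its denominator, so it cannot separate full compliance from partial take-up

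*Protocol*

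**What the plan says.** The Compliance part of the Analysis plan states its aim: "We will explore the influence of trial arm allocation compliance". Its main analysis compares carers who attended at least one session with carers who attended none, at individual level. It then adds a household measure: "attendance as a proportion of household members (e.g., two out of four household members attending means 0.5 attendance". This measure is to be used "as an instrumental variable in outcomes, as well as the attendance of children at WRAP sessions". Nothing limits the count to members who are allowed to attend.

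The Inclusion criteria set an age floor for sessions: "Children must be aged nine and over". They also say that "families with younger children can still be randomised (the adult(s) can attend WRAP". A footnote there gives the reason for the floor: "Delivering WRAP to children younger than nine years would require specific permission". Under Randomisation, referral covers the whole family: "This means all household members in the intervention group will be referred".

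**The concern.** A compliance measure should reach its maximum when everyone who can take up the offer does so. This one cannot reach 1 in any household with a child under nine, however fully the family complies. Its value therefore mixes two things: how many eligible members attended, and how many members were too young to attend.

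The consequence is clearest in the usual instrumental-variable analysis, with allocation as instrument and attendance as exposure. The intention-to-treat effect is divided by the difference in mean attendance between arms. Members who can never attend make that difference smaller, so the effect per unit of attendance grows. The unit itself, every member attending, is out of reach for those households.

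**Working it through.** **1. The plan's own figure.** Two attenders out of four members: 2/4 = 0.5. It reproduces.

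**2. The same rule in three households.**

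| Household | Attend | All-member share | Eligible-member share |
|---|---|---|---|
| Four members, all eligible | 2 | 2/4 = 0.50 | 2/4 = 0.50 |
| Two adults, two children under nine | 2 | 2/4 = 0.50 | 2/2 = 1.00 |
| One adult, three children under nine | 1 | 1/4 = 0.25 | 1/1 = 1.00 |

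The first two rows score alike on the protocol's measure, although one family took up half of what it could and the other all of it.

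**3. Household composition.** The summary table at the front gives "178 fostering households with 311 foster carers, 544 foster children, 25 other adults, 59 birth children".
- Adults per household: (311 + 25)/178 = 1.89.
- Children per household from the same table: (544 + 59)/178 = 3.39.
- Children per household from the text: 1.88 foster children (Exclusion criteria) + 1/3 birth child (Participants) = 2.21.

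The two child counts disagree, so both are carried through.

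**4. Formula.** Let a be adults, c children, and f the proportion of children under nine. The ineligible share is s = f × c/(a + c), so the highest average all-member share is 1 − s. If d is the arm contrast in eligible-member attendance, the all-member contrast is about d(1 − s), and the effect per unit is multiplied by 1/(1 − s).

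**5. Results.** The documents do not state f; 20% to 50% is an assumption.

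| f | s (c = 2.21) | Factor | s (c = 3.39) | Factor |
|---|---|---|---|---|
| 20% | 0.11 | 1.12 | 0.13 | 1.15 |
| 30% | 0.16 | 1.19 | 0.19 | 1.24 |
| 40% | 0.22 | 1.28 | 0.26 | 1.35 |
| 50% | 0.27 | 1.37 | 0.32 | 1.47 |

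**6. On the trial's own assumptions.** The Randomisation section assumes 95% receipt in the intervention arm and 2% in the control arm. If every eligible member of a receiving household attends, the eligible-member contrast is 0.95 − 0.02 = 0.93. With 3.39 children, the all-member contrast falls to 0.93 × 0.872 = 0.81 at f = 20% and 0.93 × 0.743 = 0.69 at f = 40%. Taking the minimum detectable effect of 0.37 SD purely as an example of an intention-to-treat effect, the effect per unit is 0.37/0.93 = 0.40 SD on the eligible-member scale. On the all-member scale it is 0.46 SD (f = 20%) or 0.54 SD (f = 40%).

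**7. Does the inflation depend on how attendance acts?** A simulation of 400,000 households of varied size used about 1.89 adults and 3.39 children on average, 95% v 2% receipt, and 90% of eligible members attending in receiving households. The true effect per unit was 1.0.

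| f | Effect scales with eligible share: estimate on eligible / all-member share | Effect scales with all-member share: estimate on eligible / all-member share |
|---|---|---|
| 20% | 1.00 / 1.14 | 0.87 / 1.00 |
| 40% | 1.00 / 1.33 | 0.75 / 1.00 |

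The formula holds closely in the first case. In the second, the all-member share is the unbiased one.

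**The case against.** A reader might infer that the plan will overstate the effect of attendance outright, for every outcome. The documents do not support that, for four reasons.

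- **The scale is a choice.** An effect per share of the whole household is a different unit, not automatically a biased one. For a family-relationships outcome, whole-household reach is a defensible dose, and referral does cover the whole household. The last column of the simulation shows no bias if the effect really works on that scale. This stands: the inflation is relative to full attendance by those able to attend.
- **The text calls the share the instrument.** Taken literally, the simple division does not arise. This stands as a condition on the size. It does not rescue the measure, because on the literal reading the score would carry household age mix straight into the analysis, and the Randomisation section itself links older age to placement instability.
- **No confounding of the arms.** A reader might also infer that young children bias the comparison between arms. With allocation as instrument, age mix is fixed before randomisation and balanced in expectation. It changes the scale of the first stage, not the fairness of the contrast.
- **It is a derivation detail, and the example is correct as arithmetic.** Two of four is 0.5 for four eligible members. But the protocol has not left the matter open: it states the denominator and illustrates it, and the stated rule conflicts with the purpose of the section it stands in.

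**Conclusion.** The point holds as a defect in a supplementary compliance measure. Dividing by all members gives fully compliant families with under-nines a score below 1 and makes them indistinguishable from families with partial take-up. That follows from the text alone.

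The inflation of the per-unit effect is conditional. It needs allocation as instrument, the share as exposure, and an effect that scales with attendance by those able to attend. Under those conditions the factor is about 1.12 to 1.37 with 2.21 children per household and 1.15 to 1.47 with 3.39, for an assumed 20% to 50% of children under nine. The true proportion is unknown, so the range is illustrative.

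The primary intention-to-treat result, the other intention-to-treat results and the main carer-level compliance analysis do not use this variable and are unaffected. The measure should be corrected, but no main conclusion of the trial depends on it.

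**What to change.** In the Compliance section, define the household share as members attending at least one session divided by members eligible to attend under the protocol's own age rule, that is, adults plus children aged nine and over.

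Use the same people above and below the line. Eligibility judged only on the day of randomisation would let the share exceed 1, because delivery runs to June 2024, children will turn nine, and the Randomisation section expects children to move into randomised households. So take household members at randomisation, and count a child as eligible if they reach nine before the household's delivery period ends. Fix that end date by the same rule in both arms, since control households have no delivery period of their own. Children who join later count in neither part and can be reported separately.

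Add to the worked example that all four members are eligible. Keep the all-member share, if wanted, as a descriptive measure of household reach.

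The cost is a few sentences. Annex 3 already requests dates of birth for foster and other children at randomisation, so no new data are needed.

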- 2% of control group households will receive WRAP despite being allocated to the 'do not receive intervention' trial arm. This is based on trial arm non-compliance from previous children's social care RCT experience.
- 95% of intervention group receive intervention. This is estimated to be high, given that all households have expressed interest in the intervention.
- Upon administration of the endline survey, 5% of carers are untraceable. This is based on previous children's social care RCT experience.
- By the point of the endline survey, 2% of households withdraw consent. This is based on previous children's social care RCT experience.
- For the primary outcome, 5% have implausible or missing values. We anticipate this being low, as we will primarily rely on an online survey for our primary outcome with set response options.
- 20% of carers do not respond to the endline survey. We anticipate that this will be low due to the use of an incentive voucher, social worker engagement in advance of survey distribution, and a schedule of reminder text messages.

Figure 2. Consort diagram showing participants' journey through the pilot RCT of Barnardo's WRAP programme

To randomise we will set up a system where local authorities provide to Coram by email a unique family ID for each family expressing interest (consenting to participate in the

programme and study). Randomisation will be stratified by local authority. This will include fields to enable us to check whether local authorities have applied the eligibility criteria correctly, before we undertake randomisations (box 1).

We anticipate randomising around 178 households using a securely stored spreadsheet pre-populated with randomisation outcomes, and return the outcomes back to local authorities and Barnardo's within 24 hours. We will do this for the stock of families in March 2023, and then on demand as needed for the in-flow of newly eligible families thereafter until early 2024.

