After attending an information session run by Barnardo's delivery staff, interested carers will be able to express interest in (consent to) their family's participation in the programme and evaluation. It will also be possible for carers to express interest without attending an information session. One or both (in couples) carers consenting will be taken as the whole family consenting to take part in the programme and evaluation (including Coram gathering administrative data on the family), though actual participation in WRAP is voluntary, as is our primary data gathering.

We will seek consent (paper, electronic or verbal, based on talking through the consent form) from participants ahead of or at the start of interviews and observations. After receiving contact details from local authorities, we will provide a copy of our information sheet and consent form to potential interviewees, or describe the content of these verbally. Where we are seeking an interview with a child/young person, we will provide or describe the child/young person versions of these documents. As we believe that consent should be ongoing, we will check that they have understood information sheets and will verbally check consent at the start of interviews and observations. During fieldwork the researcher will also be mindful of any signs or nonverbal cues that the participant is not comfortable or non-consensual. The participant will be reminded that they can take a break or withdraw from the research at any point without giving a reason. Consent will also be sought for any recording

of interviews. In the case of interviews with children below the age of 16, we will check for the consent of the carer in addition to their own.

We will send an online survey link by email to social workers working with families in the three local authorities, and to carers by email, post or text message. We will make clear in the front page of the survey that participation is voluntary. We will ask survey responders for consent at the start of the survey. If they do not provide their consent to participate at the start of the survey, the survey will redirect away from the questions, so they will not be asked to complete the questions and no data will be collected.

Avoiding harm

Previous research has not found serious harmful impacts of WRAP among other groups, so we do not anticipate the fostering and kinship community will experience harm as a result of participation in the intervention.

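### The Compliance section names attendance, which is voluntary and post-randomisation, as the instrumental variable and never names random allocation; the roles should be corrected (should-fix; intention-to-treat result unaffected)

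*Protocol*

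**What the plan says.** The relevant text is in the protocol's Analysis plan, under Compliance, within the other evaluation questions.

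- The section opens by saying that compliance with allocation will be explored "by including the number of sessions attended in an instrumental variable analysis". The role of the session count in that analysis is not stated.
- The main contrast is binary and at carer level: "Our compliance analysis will look at carer attendance of at least one WRAP session versus non-attendance". It is to be examined in terms of change in the primary outcome.
- A household measure follows: "We will also look at attendance as a proportion of household members". Its role is given explicitly: "attending means 0.5 attendance) as an instrumental variable in outcomes".
- The optional dosage analysis is stated as: "We may conduct an exploratory dosage analysis with the number of sessions as the instrumental variable, as opposed to binary non-/attendance". The closing comparison implies that binary attendance is otherwise the instrument.

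Two other places bear on the point. Under Randomisation, what is randomised is the family's referral: "Families who express an interest in taking part in the WRAP programme and its evaluation will be randomised to either a referral, or usual support". Under Consent, a carer's expression of interest covers the whole family, "though actual participation in WRAP is voluntary, as is our primary data gathering". The randomisation assumptions also state that "95% of intervention group receive intervention", and that 2% of control households will receive WRAP.

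**The concern.** An instrument must be independent of the unmeasured causes of the outcome and must affect the outcome only through the exposure. Family allocation meets the first condition by design. Attendance, session count and household share do not: people decide whether and how often to attend after allocation, and those decisions may track wellbeing or expected change. They are the exposure whose effect is wanted.

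If the text is followed literally, the estimate of the effect of receiving WRAP is no longer protected by randomisation, yet it would be reported under a label that tells readers it is. The carer-level contrast on the primary outcome and the household-share analysis are both firm commitments; only the dosage analysis is optional. The protocol also presents the trial as informing a future full-scale RCT, so an estimated effect of receipt may be carried forward.

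**Working it through.** **1. What the stated method reduces to.** With instrument Z, exposure D and outcome Y, the simple instrumental variable estimator is cov(Z,Y)/cov(Z,D). Setting Z = D gives cov(D,Y)/var(D), the ordinary regression slope on attendance. No protection from randomisation remains.

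**2. The plan's own benchmark.** The Compliance section states no figure. The nearest is the minimum detectable effect size (MDES) of 0.37 (0.11–0.63). From Annex 2: ICC 0.4, level-1 R² 0.6, level-2 R² 0, 1.9 adults per household, 41.3 × 3 = 123.9 households, equal split.

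- SE = √[0.4/(0.25 × 123.9) + 0.6 × 0.4/(0.25 × 123.9 × 1.9)] = √(0.01291 + 0.00408) = 0.130.
- With df = 3 × (41.3 − 2) = 117.9, the multiplier is t(0.975) + t(0.80), about 2.825.
- MDES = 0.368 (0.110–0.626). The stated figure reproduces.

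**3. Size of the spurious effect, true effect zero.** The protocol gives no selection parameters, so everything here beyond the ICC, the 95% uptake and the 2% crossover is assumed.

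*Closed form.* Let the household wellbeing component have SD √0.4 and correlate r = 0.5 (assumed) with willingness to attend. Let u be uptake in the intervention arm, with no crossover, so that P = u/2 is the share attending overall. The attender minus non-attender difference is

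r × √0.4 × ½φ(z_u) / [P(1 − P)], where φ is the normal density at the uptake cut-off.

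At u = 0.95: φ = 0.1031, P = 0.475, so 0.5 × 0.632 × 0.0516/0.2494 = 0.065, or 0.07 SD. If the 2% of control households that cross over are the most willing ones, the figure becomes 0.10 SD.

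*Fixed gap.* If those who would never attend score 0.3 SD lower (assumed), with 2% crossover: at 95% uptake, never-attenders make up 0.025 + 0.025 = 0.05 of the sample and all non-attenders 0.025 + 0.49 = 0.515, so the difference is 0.3 × 0.05/0.515 = 0.03 SD.

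*Simulations.* Each used 124 households of two adults, ICC 0.4 and 800 trials per setting. One selected on household wellbeing (r = 0.5). The other selected on an individual trait (correlation 0.6 with propensity to attend; trait–outcome loading 0.2 or 0.4) with 2% crossover.

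Spurious effect in SD, endline scores, binary attendance:

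| Uptake | Household trait, closed form | Household trait, simulated | Fixed 0.3 SD gap | Individual trait, simulated |
|---|---|---|---|---|
| 95% | 0.07–0.10 | 0.08 | 0.03 | 0.03–0.06 |
| 80% | 0.18–0.21 | 0.19 | 0.10 | 0.06–0.13 |
| 60% | 0.29–0.32 | 0.30 | 0.17 | 0.09–0.19 |

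In the individual-trait simulation, using session count as the instrument for binary attendance gave 0.08–0.18 SD at 95% uptake. Allocation as the instrument gave about zero in both simulations.

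**4. Change scores.** The carer contrast is described in terms of change. A further simulation (same household structure, r = 0.5, 2% crossover, within-person baseline–endline correlation 0.75 assumed, 3,000 trials per setting) gave, at 95%, 80% and 60% uptake:

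- endline scores: 0.07, 0.18, 0.29 SD;
- change scores, household level stable over time: about 0.00 throughout, false positives 5–6%;
- change scores, household level correlated 0.8 over time: 0.01, 0.04, 0.06 SD, false positives 6–9%.

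**5. After correction.** With allocation as the instrument, the first stage on the protocol's assumptions is 0.95 − 0.02 = 0.93. The complier effect is the intention-to-treat effect divided by 0.93 (× 1.075), so 0.37 SD would correspond to about 0.40 SD. Little precision is lost. These uptake figures are framed by arm and household, so a carer-level first stage could be weaker.

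**The case against.** The best defence is that this is a slip of terminology. The section's opening sentence fits session count as the instrumented exposure, and the author may have written instrumental for instrumented. That is plausible. But the later text assigns the instrument role to attendance twice, and nothing names allocation, so an analyst following the protocol would do the wrong thing. Nor is this a detail left to a later analysis plan: the protocol states a rule.

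A second defence is that little depends on the section. This stands in large part. The analyses are supplementary, the dosage analysis is optional and exploratory, and the intention-to-treat conclusion, sample size, alpha and multiplicity rule do not draw on them. That argues for a lower severity, not for leaving the text.

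Readers might infer more than the documents support:

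- *That the bias is around 0.30 SD with a 50% false-positive rate.* Those values come from one assumed selection model at 60% uptake on endline scores. The protocol assumes 95%, where the same model gives 0.08 SD and 9%, and it specifies change for the carer contrast.
- *That the bias must flatter WRAP.* Carers with poorer wellbeing might attend more, reversing the sign. The protocol does not say.
- *That the household share counts children under nine, who cannot attend.* The denominator is described only as household members and is not defined; that detail can be settled later.
- *That carer-level attendance is the wrong exposure.* A relative's attendance may affect a non-attending carer, which strains the exclusion restriction even with the right instrument. But the protocol already plans a household measure alongside, and which exposure leads is a matter of choice.

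The 95% assumption is not a guarantee either: the protocol's own risk table rates a shortfall in recruitment and retention in WRAP as high in both likelihood and impact.

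**Conclusion.** The point holds in a limited form. As written, the Compliance section makes attendance the instrument and omits random allocation. Followed literally, it gives an as-treated comparison open to self-selection. The primary intention-to-treat analysis is unaffected.

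Size and direction rest on selection and uptake that the protocol does not give. Under the illustrative assumptions above, binary attendance carries about 0.03 to 0.08 SD at 95% uptake (0.10 if crossover is concentrated in the most willing households), against an MDES of 0.37. It is larger at lower uptake, and close to zero where change scores are analysed and selection is on a stable wellbeing level. Selection on expected change could still bias change scores. The documents do not support a claim of large or certain bias.

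Severity: should-fix.

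**What to change.** Rewrite the Compliance section so that:

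- randomised family allocation is the instrument;
- attendance is the endogenous exposure, in each planned form (at least one session, number of sessions, household share);
- estimation is by two-stage least squares with the primary model's covariates and household-clustered standard errors;
- direct attender versus non-attender contrasts, if shown, are labelled descriptive and not presented as causal effects.

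Optionally, add a household-level exposure (any member attended), because a relative's attendance may affect a carer who did not attend.

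The cost is wording only. Attendance and session counts are already requested from the delivery organisation and in the final data returns (Annex 3), and allocation is held by the evaluator.
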